If  $\geq 2$  of the first 3 patients or  $\geq 2$  of 6 patients have DLTs during cycle 1, we will perform safety (detailed toxicity) review to assess for disease versus treatment-related toxicities. Given that pembrolizumab is given only once in cycle 1 (day 8), we will first dose de-escalate azacitidine to 75 mg/m^2 x 5 days. However, if the safety data analysis suggests that the toxicities are more likely pembrolizumab related, an alternative approach we may take is to exclude pembrolizumab in cycle 1 and start pembrolizumab dosing in cycle 2 when AML is better controlled but maintain azacitidine dose/schedule. If  $\leq 1$  of the 6 patients experience DLTs during cycle 1 but  $\geq 2$  of 6 patients experience DLTs during cycle 2 and cycle 3 or cycle 1, 2 and 3, we will first dose de-escalate pembrolizumab to 200 mg given every 4 weeks starting on Day 1 of Cycle 2 and maintain azacitidine dose/schedule. When each dose de-escalation occurs, additional 6 patients will be enrolled at that dose level. For the details of dose de-

[figure not shown]
escalation, please see Section 2.2 Trial Diagram.

Only after safe dose/schedule is defined ( $\leq 1$  of 6 patients having DLT in cycle 1-3) we will start enrollment in the phase 2 cohorts. A full safety assessment of the combination of AZA and pembrolizumab will be performed in all patients after 1, 2, and 3 cycles and in subsequent cycles according to the NCI Common Terminology Criteria for Adverse Events (CTCAE), version 4.0. For efficacy analysis, those patients who were treated at dose/schedule selected for Phase 2 will be included.

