Bone marrow biopsy/aspirate will be performed after 2 and 6 cycles of therapy, and every 3-6 months thereafter as described in Section 6.0 Trial Flow Chart. Treatment with azacitidine/pembrolizumab will continue until confirmed disease progression, unacceptable toxicity, or if patient is withdrawn from study for other reasons (Section 5.9). Patients having a clinical benefit from this treatment combination including CR/CRI but also those who achieve response less than CR/CRI (ie., PR/MLFS/HI/SD) will be able to continue on treatment on clinical study (AZA and pembrolizumab) until they meet criteria specified in section 5.9. After the end of treatment, each subject will be followed for 30 days for AEs monitoring (serious adverse events will be collected for 90 days after the end of treatment as described in Section 7.2.3.3.2.). Subjects who discontinue treatment for reasons other than disease progression will have post-treatment follow up for disease status until disease progression, initiating non-study cancer treatment, withdrawing consent or becoming lost for follow up. All subjects will be followed for overall survival until death, withdrawal of consent or the end of the study, whichever comes first.

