### **5.10 Subject Replacement Strategy**

#### **Safety Run In Phase:**

- If laboratory abnormalities and clinical situation exist on day 8 during cycle 1 precluding pembrolizumab administration, pembrolizumab administration can be delayed for 2 weeks, up to day 22, provided laboratory abnormalities correct themselves to the levels defined in Section 5.1 and clinical situation resolves/improves.

Patients who are ineligible for pembrolizumab administration by day 22 of cycle 1 will be removed from the study and replaced by another subject.

- If subject discontinue study treatment for any reason other than drug-related toxicity prior to completing 2 study cycles, this subject will be replaced.
- If subject discontinue study treatment before receiving a single dose of pembrolizumab, this subject will be replaced.

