Note: If increase in WBC is not leukemia-related such as seen with the use of steroids, infections, or growth factors and does not require hydroxyurea patient can remain on the study.

3. New CNS leukemia or new extramedullary disease.
4. Progressive disease is usually accompanied by a decline in ANC and platelets and increased transfusion requirement and decline in performance status or increase in symptoms. Patient can be removed from the study before cycle 6 at the discretion of the investigator / treating physician if in their assessment further treatment on the study would not be in patient's best interest. This should be discussed with the Protocol Chair and the reason for study treatment discontinuation at any time should be documented and confirmed by BM assessment. (Note: the goal is to administer at minimum 2 cycles of therapy before initial assessment.)

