$\leq 1$  of the 6 patients experience DLTs during cycle 1 but  $\geq 2$  of 6 patients experience DLTs during cycle 2 and cycle 3, or cycle 1, 2 and 3, we will first dose de-escalate pembrolizumab as described in Section 2.2 and maintain azacitidine dose/schedule. When each dose de-escalation occurs (maximum 2), additional 6 patients will be enrolled at that dose level. For the details of dose de-escalation, please see Section 2.1 and 2.2 Trial Diagram.

Only after a safe dose/schedule is defined will we start enrollment in the phase 2 cohorts. A full safety assessment of the combination of AZA and pembrolizumab will be performed in all patients after 1, 2 and 3 cycles and in subsequent cycles according to the NCI Common Terminology Criteria for Adverse Events (CTCAE), version 4.0. Patients who are treated at dose/schedule selected for Phase 2 will be included in the primary efficacy analysis and the analyses of secondary and exploratory objectives.

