### 8.2.2 Sample Size

The primary objective of this study is to estimate the complete response (CR/CRi) rate in each cohort. We estimated sample sizes for the 2 cohorts using a one-sample, one-sided binomial test, with Type I and Type II errors of 0.05 and 0.2, respectively. For Cohort 1, the null and expected response rates were taken to be 0.1 and 0.25, respectively. For Cohort 2, the null and expected response rates were taken to be 0.17 and 0.34, respectively. The sample sizes were calculated to be 38 (which will be rounded to 40) and 40 for Cohorts 1 and 2, respectively.

We used an efficient and flexible design based on Bayesian predictive probability (Lee and Liu, 2008). This design controls the type I and type II error rates and also allows flexible monitoring for futility and efficacy of the new treatment. Furthermore, this design also has better sampling properties than Simon's 2-stage design, i.e. probabilities of early termination for futility under the null hypothesis and for efficacy under the alternate hypothesis are higher and the expected sample size is lower than Simon's 2-stage design.

The following input parameters were assumed in our design: minimum and maximum number of patients was 10 and 40, respectively. Type I and II errors were 0.1 and 0.2, respectively. For cohort 1, the treatment effect for current standard was 0.1 (i.e., probability of CR/CRi) and expected treatment effect for the new treatment was 0.25. For cohort 2, the treatment effect for current standard was 0.17 and expected treatment effect for the new treatment was 0.34. A beta (0.25, 0.75) distribution was assumed for the prior for the expected effect of the new treatment. This is a weak prior, which has negligible effect on the stopping boundaries.

The stopping boundaries for futility are given in the tables below for cohorts 1 and 2. For example, the first row of Table 1 indicates that we would stop the trial for futility if we see 0 responses (CR/CRi) out of the first 10 patients after 6 cycles of therapy (to be evaluable for futility pts must complete at least 2 cycles of therapy); if the study was not stopped after 10 patients, the next evaluation will be done after 14 patients (2nd row). Study will be stopped for futility if we see 1 response or less for futility. If the study continues, the next evaluation happens after 21 patients (3rd row). Study will be stopped if we see 2 or fewer responses in the first 21 patients.

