Cohort 1: Interim monitoring boundaries for stopping for futility.

Patient. No.	Futility boundary (less than or equal to)
10	0
14	1
21	2
27	3
32	4
36	5
40	6

Cohort 2: Interim monitoring boundaries for stopping for futility.

Patient. No.	Futility boundary (less than or equal to)
10	0
11	1
16	2
20	3
24	4
27	5
31	6
34	7
36	8
39	9
40	10

For cohort 1, the expected sample size under the null and alternative hypotheses is 17.7 and 18.3, respectively. For cohort 2, these were 19.2 and 21.0.

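### Does counting only patients who complete 2 cycles at the futility looks require a change, when the primary analysis counts all treated patients?

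*Combined protocol and SAP*

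**What the plan says.** Section 8.2.2 sets futility boundaries at 7 patient counts in Cohort 1 and 11 in Cohort 2. Patients enter those counts under a condition: "to be evaluable for futility pts must complete at least 2 cycles of therapy". The design inputs state that the "minimum and maximum number of patients was 10 and 40, respectively". The operating characteristics follow the tables: "For cohort 1, the expected sample size under the null and alternative hypotheses is 17.7 and 18.3, respectively", with 19.2 and 21.0 for Cohort 2.

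The primary analysis set is wider. Section 2.1 says: "For efficacy analysis, those patients who were treated at dose/schedule selected for Phase 2 will be included". Section 8.2.1 says the same: "Patients who are treated at dose/schedule selected for Phase 2 will be included in the primary efficacy analysis". Section 8.2.3 adds no minimum exposure.

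Three other places bear on the point.

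- Section 2.1 on assessment timing: "Bone marrow biopsy/aspirate will be performed after 2 and 6 cycles of therapy".
- Section 7.1.2.6 on early removal for progression: "the goal is to administer at minimum 2 cycles of therapy before initial assessment".
- Section 5.10, under the safety run-in only: "If subject discontinue study treatment for any reason other than drug-related toxicity prior to completing 2 study cycles, this subject will be replaced". Nothing equivalent is given for the rest of either cohort.

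**The concern.** The futility rule and the primary estimate use different denominators for the same endpoint. The first routine response marrow follows cycle 2, so patients who leave earlier are nearly all non-responders. Leaving them out has two effects:

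- It raises the response rate compared with each boundary, if the null rates were meant for all treated patients.
- With at most 40 treated and no replacement after the run-in, fewer than 40 patients are evaluable, so later rows may not be reached.

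Both effects make early stopping at the null less likely than under the printed design, and more patients would receive an ineffective regimen. A reader might also take a cohort's full accrual as stronger evidence of activity than it is.

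**Working it through.** **Inputs.** From section 8.2.2: null and expected rates of 0.10 and 0.25 (Cohort 1) and 0.17 and 0.34 (Cohort 2); a beta(0.25, 0.75) prior; 10 to 40 patients; the printed boundaries. The share d lost before 2 cycles is not in the documents. It is assumed to be 5% to 30%, with all lost patients non-responders. The entry requirement of at least 12 weeks' life expectancy (section 5.1.2) favours the lower end.

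**1. The plan's own figures.** The thresholds of the predictive-probability design are not printed, so they were searched. Success at 40 was defined as a posterior probability above 0.90 that the rate exceeds the null. The efficacy cut-off was 0.95 and the futility cut-off 0.11 (Cohort 1) or 0.05 (Cohort 2), with a look after every patient from the 10th. These values return both printed tables exactly. Expected sizes are 17.70 and 18.35 (Cohort 1) and 19.16 and 20.97 (Cohort 2), against the printed 17.7 and 18.3, and 19.2 and 21.0. The printed figures therefore fit a design in which every patient counts.

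**2. Effect of exclusions at the null.** Each treated patient is lost with probability d, is an evaluable responder with probability r, or is an evaluable non-responder with probability 1 − d − r. A look occurs when the evaluable count reaches a row. The recursion is exact, uses the printed futility rows only, and stops at 40 treated.

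- Reading A: the null rate p refers to all treated. Then r = p, and the counted rate is p/(1 − d).
- Reading B: p refers to 2-cycle completers. Then r = p(1 − d), and the counted rate is p.

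First row of Cohort 1 under reading A with d = 0.20: the counted rate is 0.10/0.80 = 0.125. The chance of 0 responses in 10 falls from 0.90^10 = 0.349 to 0.875^10 = 0.263.

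Probability of a futility stop before the 40th treated patient, at the null:

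| d | Cohort 1, A | Cohort 1, B | Cohort 2, A | Cohort 2, B |
|---|---|---|---|---|
| 0 | 0.898 | 0.898 | 0.916 | 0.916 |
| 5% | 0.871 | 0.892 | 0.857 | 0.886 |
| 10% | 0.821 | 0.870 | 0.785 | 0.858 |
| 20% | 0.693 | 0.820 | 0.606 | 0.796 |
| 30% | 0.545 | 0.767 | 0.413 | 0.736 |

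Under A with d = 20%, mean treated rises from 19.1 to 25.8 (Cohort 1) and from 20.3 to 28.4 (Cohort 2). The cap is only one of the two causes. At d = 20%, lost looks alone give 0.820 and 0.796 (reading B). The raised rate alone, with 40 evaluable patients, gives 0.787 and 0.761.

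**3. False passing.** Apply the last row to all 40 treated patients under A. Passing at the null goes from 0.069 to 0.081, 0.089 and 0.094 (Cohort 1), and from 0.054 to 0.060, 0.063 and 0.065 (Cohort 2), for d = 10%, 20% and 30%. It cannot exceed P(X ≥ 7 | 40, 0.10) = 0.0995 or P(X ≥ 11 | 40, 0.17) = 0.066. Both are within the type I error of 0.1 set for this design.

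**4. The alternative rule at the expected rates.** Count everyone treated, with early leavers as non-responders. If 0.25 and 0.34 refer to all treated, early stopping is 0.18 in both cohorts. If they refer to 2-cycle completers, the probability of stopping an effective regimen early is:

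| d | Cohort 1, rule as written | Cohort 1, all treated | Cohort 2, rule as written | Cohort 2, all treated |
|---|---|---|---|---|
| 10% | 0.173 | 0.266 | 0.153 | 0.299 |
| 20% | 0.160 | 0.375 | 0.135 | 0.457 |
| 30% | 0.148 | 0.506 | 0.123 | 0.635 |

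**Limit.** Steps 2 to 4 take outcomes as known at each look. Section 8.2.2 judges response after 6 cycles. A simulation with 40 patients accruing evenly over the planned 24 months, outcomes at 6 months and early losses known at 1 month gives, under A with d = 10%, about 0.79 counting all treated against 0.69 as written (Cohort 1), and 0.77 against 0.64 (Cohort 2). The absolute levels drop, but a gap of similar size remains.

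**The case for a change.** The strongest case for acting is that the direction does not depend on the reading: with any loss before 2 cycles, every variant tried stops less often at the null than the printed design. A deliberate evaluability rule should come with operating characteristics that match it. Cohort 1 enrolled its full 40 (section 5.1.1), and how much that says about activity depends on who was counted at the looks. Section 10.5 already asks for reporting against prearranged statistical goals, and a table would cost little.

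The mismatch stands as a matter of fact. It does not follow that the rule is wrong. Section 7.1.2.6 explains that azacitidine usually needs 4 to 6 cycles for its full effect and that immune activation may take weeks to months. Judging futility on adequately treated patients while estimating the endpoint on all treated is a coherent pairing of two sets for two purposes. Which denominator is better depends on what the null and expected rates describe, and the documents do not say. Re-tabulating past looks on another denominator would be post hoc and would alter no decision. Uniform loss may also overstate the effect in Cohort 1, because most early leavers in the run-in were to be replaced.

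**Conclusion.** No change to the plan. The rule lowers early futility stopping at the null by an amount that rests on two unknowns: the share lost before 2 cycles and the denominator of the null rates. At 5% lost with completer-based rates, the fall in Cohort 1 is from 0.898 to 0.892, which is negligible. At 30% lost with all-treated rates it is large in both cohorts. Against that, counting everyone could raise wrongful early stopping to as much as 0.506 and 0.635, so the choice is a fair trade-off.

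The practical consequence is nil. The CR/CRi estimate and its exact interval use all patients treated at the Phase 2 dose and schedule whichever futility rule is used. Removals for toxicity have their own stopping rule in section 8.2.2.1. Cohort 1 is complete, and Cohort 2 was closed on risk-benefit information from the FDA (section 5.1.1). What remains is a gap that analysts fill sensibly when reporting: which denominator the design rates refer to, and which patients were counted or excluded at each look.

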##### Cohort #1

1. Have histologically or cytologically confirmed relapsed or refractory AML (i.e.  $\geq 5\%$  blasts by manual differential on bone marrow aspirate/biopsy/flow cytometry), excluding acute promyelocytic leukemia (APL; FAB M3; t(15;17)).
2. Be willing and able to provide written informed consent/assent for the trial.
3. Be  $\geq 18$  years of age on day of signing informed consent.
4. Not be appropriate candidate for intensive salvage chemotherapy due to co-morbidities or other disease- or treatment-related factors.

NOTE: Subjects who received prior treatment with hypomethylating agents either for Myelodysplastic Syndrome (MDS), Myeloproliferative Neoplasm (MPN), or AML will be eligible.

NOTE: Subjects who had prior allogeneic stem cell transplant (alloHSCT) will be eligible as long as they have been at least 3 months after allogeneic HSCT and are off of all immune suppression for at least 3 weeks ( $>21$  days) and have no evidence of active graft versus

host disease (GVHD). Subjects with prior alloHSCT will NOT be eligible for enrollment during the safety run in phase.

5. Demonstrate adequate organ function as defined in Table 1, all screening labs should be performed within 14 days of treatment initiation.
6. ECOG performance status < 2.
7. A projected life expectancy of at least 12 weeks.
8. Female subject of childbearing potential should have a negative urine or serum pregnancy within 72 hours prior to receiving the first dose of study medication. If the urine test is positive or cannot be confirmed as negative, a serum pregnancy test will be required.
9. Female subjects of childbearing potential (Section 5.8.2) must be willing to use an adequate method of contraception as outlined in Section 5.8.2 – Contraception, for the course of the study through 120 days after the last dose of study medication.

Note: Abstinence is acceptable if this is the usual lifestyle and preferred contraception for the subject.

10. Male subjects of childbearing potential (Section 5.8.2) must agree to use an adequate method of contraception as outlined in Section 5.8.2- Contraception, starting with the first dose of study therapy through 120 days after the last dose of study therapy.

Note: Abstinence is acceptable if this is the usual lifestyle and preferred contraception for the subject.

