Progression is not a useful concept for monitoring in AML. Further, pembrolizumab is expected to trigger immune-mediated responses, which require activation of the immune system prior to the observation of clinical responses. Such immune activation may take weeks to months to be evident. Azacitidine is a low-intensity chemotherapy agent that usually requires at least 4-6 cycles of therapy to exert its full anti-leukemia effect. Thus, some patients may have objective increase in leukemia burden or other disease parameters within weeks following the start of pembrolizumab/azacitidine dosing. Such patients may not have had sufficient time to develop the required immune activation or for azacitidine/pembrolizumab to exert their anti-leukemia effect. In conventional studies, such increase in leukemia burden (bone marrow, peripheral blood, extramedullary disease) or other disease parameters during the first 2-4 months of the study would constitute progressive disease as per above criteria and lead to premature discontinuation of therapy, thus disregarding the potential for subsequent immune-mediated clinical response. Therefore, patients with leukemia progression by bone marrow or peripheral blood laboratory parameters prior to completion of 6 cycles of therapy but without rapid clinical deterioration and who do not require additional immediate therapy,

may continue to be treated with pembrolizumab /azacitidine and clinically observed to allow detection of a subsequent tumor response. Subjects that meet the PD criteria and continue on study therapy must discontinue azacitidine/pembrolizumab if there are no signs of disease stabilization by end of 6 cycles of therapy (approximately 6 months). The date of progression will be defined as of the first observation date of progressive disease in those patients who do not upgrade response with continuous therapy.

However, we are still using progression of AML as a reason for early discontinuation of study treatment (before completing 6 cycles) with the following criteria:

1. Progression of the leukemia such that clinical sequelae would result from a high WBC blast count such as hyperleukocytosis, or due to increasing size of spleen or extramedullary disease..
2. Failure to achieve  $WBC \leq 30 \times 10^9/L$  off hydroxyurea after 2 cycles of therapy.

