### 8.2.3 Analysis of Primary Endpoint

The primary objective of this study is to estimate the complete remission (CR/CRI) rate of AZA followed by pembrolizumab in 1) relapsed/refractory AML patients, and 2) older ( $\geq 65$  years) newly diagnosed AML patients not candidates for intensive induction chemotherapy. The CR/CRI rate will be reported with an exact binomial, two-sided, 95% confidence interval, separately by each cohort. We will test for heterogeneity of the treatment effect between cohorts using an interaction test, and if there is no evidence of heterogeneity, we will pool all patients treated at the phase II dose/schedule and estimate the CR/CRI rate with an exact binomial, two-sided, 95% confidence interval.

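### The futility count in 8.2.2 drops patients who stop for leukemia before 2 cycles, while 8.2.1 keeps them in the efficacy analysis; the futility rule then stops an inactive regimen somewhat less often than printed

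*Combined protocol and SAP*

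**What the plan says.** Section 8.2.2 prints futility rows for each cohort under the title "Interim monitoring boundaries for stopping for futility". It states the design's error rates: "Type I and II errors were 0.1 and 0.2, respectively". The patients counted at those rows are limited by one condition: "to be evaluable for futility pts must complete at least 2 cycles of therapy". The reason for stopping plays no part in it.

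The efficacy population is wider. Section 8.2.1 says: "Patients who are treated at dose/schedule selected for Phase 2 will be included in the primary efficacy analysis". Section 2.1 says the same, and neither sets a minimum number of cycles.

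Section 7.1.2.6 foresees leukemia-driven stops: "we are still using progression of AML as a reason for early discontinuation of study treatment (before completing 6 cycles"). Its routes include clinical sequelae of a rising blast count, new CNS or extramedullary disease, and investigator judgment. None of these has a 2-cycle floor; two cycles is described only as an aim: "the goal is to administer at minimum 2 cycles of therapy before initial assessment".

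No other section settles how such a patient counts. The replacement rule in 5.10 is listed under the safety run-in only, and it concerns replacement, not counting. The stopping rule in 8.2.2.1 covers removal for toxicity.

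**The concern.** A patient who stops for leukemia before completing two cycles has not reached CR/CRi. Removing that patient from the futility denominator is an informative exclusion: it can only raise the response rate that the rule sees. The same patient remains in the denominator of the primary estimate.

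Such stops are plausible. The entry floor is "A projected life expectancy of at least 12 weeks", and two 28-day cycles take 8 of those 12 weeks.

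An example for Cohort 1: 14 patients treated, 4 early leukemia failures, 1 response. Under 8.2.2 as written this is 1 of 10 evaluable, above the bound of 0, so the cohort continues. With all treated patients counted it is 1 of 14, which meets the bound of 1, so the cohort stops.

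A second gap follows. Section 5.1.1 reports that Cohort 1 enrolled 40. If even one of them is not evaluable, the 40-patient row (6 or fewer) is never reached on evaluable patients, and the plan gives no rule for that case.

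**Working it through.** **Inputs (8.2.2).** Null and expected rates: 0.10 and 0.25 (Cohort 1), 0.17 and 0.34 (Cohort 2). Futility rows, as patients:bound:
- Cohort 1: 10:0, 14:1, 21:2, 27:3, 32:4, 36:5, 40:6.
- Cohort 2: 10:0, 11:1, 16:2, 20:3, 24:4, 27:5, 31:6, 34:7, 36:8, 39:9, 40:10.

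**Assumptions.** The documents give no number of early leukemia stops, so k = 1 to 8 exclusions out of 40 is a range, not an estimate. The rates 0.10 and 0.17 are taken as rates among all treated patients.

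**Method.** Let a_n(r) be the probability of r responders after n counted patients with no row crossed. Then a_n(r) = a_(n-1)(r)·(1-q) + a_(n-1)(r-1)·q. At each row, a_n(r) is set to 0 for every r at or below the bound. The sum left at the end is the chance of crossing no row, called the pass chance below.

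**Step 1: the plan as printed, nobody excluded (q = stated rate).**

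| | Pass chance, null | Pass chance, expected rate |
|---|---|---|
| Cohort 1 | 0.069 | 0.801 |
| Cohort 2 | 0.054 | 0.789 |

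This is in line with the stated 0.1 and 0.2. The printed expected sample sizes are matched only roughly under the null (19.1 against 17.7; 20.3 against 19.2). Under the alternative they are not matched by futility rows alone (36.0 against 18.3; 36.6 against 21.0). The comparison with 0.1 is therefore approximate.

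**Step 2: 40 enrolled, k excluded, last bound kept at patient 40-k.** The rate among counted patients becomes q = p·40/(40-k). For Cohort 1 with k = 4, q = 0.10·40/36 = 0.111.

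| k | Cohort 1 null pass chance |
|---|---|
| 0 | 0.0691 |
| 1 | 0.0728 |
| 2 | 0.0763 |
| 3 | 0.0792 |
| 4 | 0.0814 |
| 5 | 0.0834 |
| 6 | 0.0851 |
| 7 | 0.0865 |
| 8 | 0.0877 |

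In Cohort 2, with the bound of 10 kept, k = 1 to 8 gives 0.056-0.059 against 0.054.

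The effect is small for a simple reason. Excluded patients contribute no responses, so the last row turns on the same responder total either way; only the interim rows lose force. Even with no interim rows at all, a single look at 40 requiring at least 7 responses (Cohort 1) or 11 (Cohort 2) has null pass chances of 0.0995 and 0.066.

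**Step 3: Cohort 1, the 40-patient row not applied because 40 evaluable are never reached.** For k = 1 to 4 the null pass chance is 0.112 to 0.147. Most of this comes from losing the row. With nobody excluded, the chance of stopping before the last row is 0.898, so omitting that row alone gives 1 - 0.898 = 0.102.

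**Step 4: enrollment continued until 40 are evaluable.** With a share f dropped, q = p/(1-f).

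| f | Treated for 40 evaluable | Cohort 1 null | Cohort 2 null |
|---|---|---|---|
| 10% | 40/0.9 = 44.4 | 0.106 | 0.099 |
| 20% | 40/0.8 = 50 | 0.165 | 0.182 |

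These need more than the 40 patients per cohort that sections 1.0 and 8.2.2 allow.

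**The case against.** **A response-evaluable set for interim looks is a recognized choice.** Section 7.1.2.6 says azacitidine usually needs 4-6 cycles and immune activation weeks to months. That justifies not judging a patient still on treatment too soon. It does not justify removing one who has already stopped because of leukemia.

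**Early stops may be few.** Entry requires ECOG below 2; the WBC criterion applies only after 2 cycles; and patients with laboratory progression but no rapid deterioration may continue. This stands, and the frequency here is an assumption.

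**The reference rates may be per evaluable patient.** Section 8.2.2 does not say. If they are, counting evaluable patients causes no inflation. This stands as a condition on the figures.

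**Little can change now.** Both cohorts are closed, Cohort 2 on FDA risk-benefit information, and 8.2.3 promises an estimate: "The CR/CRI rate will be reported with an exact binomial, two-sided, 95% confidence interval". No section commits to reporting a futility verdict. This limits the value of a change.

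**A late change to the denominator is itself post hoc.** The trial is open-label and, under 10.5, the principal investigator reviews efficacy endpoints. This stands, and it is why both counts should be shown.

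A reader might infer from Step 4 that the design's type I error reaches 0.165 or 0.182. The enrollment cap rules that out. Phase 2 also has no replacement rule to carry enrollment past 40.

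**Conclusion.** The point holds as a modest flaw in the futility rule. As written, 8.2.2 drops certain non-responders that 8.2.1 and 2.1 retain, and the direction is toward stopping too seldom. Within 40 enrolled and with the last bound kept, the null chance of crossing no row is 0.073-0.088 in Cohort 1 and 0.056-0.059 in Cohort 2 for 1 to 8 exclusions, all below 0.1. In Cohort 1 it exceeds 0.1 within the cap only if the 40-patient row goes unapplied.

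This rests on an assumed number of early leukemia stops, on reading 0.10 and 0.17 as all-treated rates, and on a futility-only model that only partly reproduces the printed expected sample sizes.

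A reader might also infer that the primary result is biased, or that Cohort 1 should have stopped. The documents support neither: the CR/CRi estimate uses the all-treated set, and no response counts are given. What remains open is how the interim rule is described and whether the last Cohort 1 row is applied.

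**What to change.** 1. Add to 8.2.2 that a patient treated at the phase 2 dose/schedule who stops because of leukemia before completing 2 cycles counts as a non-responder in the futility count.
2. Judge the Cohort 1 40-patient row (6 or fewer) on all patients treated at that dose/schedule. If that set is below 40, keep the bound of 6 at the last patient and say so.
3. List the early leukemia-driven stops by cohort. Show the as-written evaluable count beside the all-treated count, labelled as a clarification made after accrual closed.

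The cost is one sentence and one listing. Section 7.1.2.6 already requires the reason for discontinuation to be documented. No treatment rule or procedure changes.

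The downside is a slightly higher chance of a futility verdict for an active regimen. At a true rate of 0.25 the Cohort 1 pass chance is 0.80, which is what the printed boundaries already give. If only 36 to 39 patients form the all-treated set, keeping the bound of 6 gives 0.765 to 0.795.
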